2.3 POTENTIAL RISKS AND BENEFITS

2.3.1 KNOWN POTENTIAL RISKS

Expected adverse events of the laser treatment procedure include transient tenderness, erythema, edema, and/or induration in the treated area lasting from one to three weeks after the treatment. In addition, other adverse events may include and include localized firmness, ecchymosis, skin burn, hyperpigmentation, hypopigmentation, blister and changes in skin laxity. Rarely, skin contour irregularities, dimpling, asymmetry (uneven appearance due to uneven anatomy or uneven treatment of the area), necrosis (tissue death), hardness and nodules occur. Protective laser eyewear will be worn by the subject and operator providing the procedure.

The device has a contact tissue cooling system in place during the procedure to minimize thermal discomfort and prevent damage to the treatment area. Expected adverse events related to the contact cooling include tingling, itching, decreased sensation, numbness, erythema and tenderness.

The boundaries of the treatment area will be marked with a semi-permanent tattoo ink using a microblade. The ink markings should dissipate within one year. Microblade marking may be associated with tenderness.

There are minimal risks associated with the use of ultrasound. The use of the ultrasound may cause redness of the skin. Skin rashes rarely occur with the use of ultrasound gel.

Risks will be mitigated by conducting this protocol with an investigator experienced in the therapeutic area of the clinical investigation. The investigator will be trained by the sponsor on the use of the device. The device design incorporates safety mechanisms which minimize risks. Patients will also be rigorously screened prior to their enrollment and rigorously followed over the course of the study.

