The normal response to this treatment is transient tenderness, edema and/or induration in the treated area which should resolve within one to two weeks. If any other side effects occur or persist for longer than expected, they must be recorded in the adverse event (AE) section of the case report form (CRF).

For post-treatment cooling and/or discomfort, cold packs can be applied to treatment area if needed with acetaminophen at recommended doses used to alleviate pain as needed.

During the day following treatment, care should be taken to prevent any mechanical or thermal damage to the treated sites: avoid hot baths, massage, contact sports, swimming, etc. The treated areas should be kept clean to avoid contamination or infection. The subject should be reminded to not make any major changes in their diet or lifestyle during the course of the study.

Subjects will be discharged from the clinic and will be scheduled to return for the six week assessment.

7.3.3 FOLLOW-UP 1

Visit 2, Week 6 (\pm 3 days)

Subjects will return to the clinic six weeks after the treatment. Adverse events, weight and any changes to concomitant medications will be recorded.

Measurement of the abdominal circumference will be made with the sponsor supplied tape measure using the marked boundaries as a guide for replication.

Photographs of the marked treatment area followed by ultrasound measurements of the marked treatment area will be made as per the instructions supplied by the sponsor.

Subjects will be discharged from the clinic and will be scheduled to return for the Twelve week (Final) assessment.

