8.2.3 EXPECTEDNESS

Expected adverse reactions are AEs that are common and known to occur for the study agent being studied. Expected adverse events of the treatment include transient tenderness, erythema, edema, and/or induration in the treated area lasting from one to three weeks after the treatment.

The device has a contact tissue cooling system in place during the procedure to minimize thermal discomfort and prevent damage to the treatment area. Expected adverse events related to the contact cooling include tingling, itching, decreased sensation, numbness, erythema and tenderness.

An AE or suspected adverse reaction is considered "unexpected" if it is not known to occur for the study treatment being studied and at the specificity or severity that has been observed.

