8.3 TIME PERIOD AND FREQUENCY FOR EVENT ASSESSMENT AND FOLLOW-UP

The occurrence of an AE or SAE may come to the attention of study personnel during study visits and interviews of a study participant presenting for medical care, or upon review by a study monitor. All AEs

including local and systemic reactions not meeting the criteria for SAEs will be captured on the appropriate CRF. Information to be collected includes event description, time of onset, clinician's assessment of severity, relationship to study product (assessed only by those with the training and authority to make a diagnosis), and time of resolution/stabilization of the event. All AEs occurring while on study must be documented appropriately regardless of relationship. All AEs will be followed to adequate resolution.

Any medical condition that is present at the time that the participant is screened will be considered as baseline and not reported as an AE. However, if the study participant's condition deteriorates at any time during the study, it will be recorded as an AE. UPs will be recorded in the data collection system throughout the study.

Changes in the severity of an AE will be documented to allow an assessment of the duration of the event at each level of severity to be performed. AEs characterized as intermittent require documentation of onset and duration of each episode.

The PI will record all reportable events with start dates occurring any time after informed consent is obtained until 7 (for non-serious AEs) or 30 days (for SAEs) after the last day of study participation. At each study visit, the investigator will inquire about the occurrence of AE/SAEs since the last visit. Events will be followed for outcome information until resolution or stabilization.

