8.4 REPORTING PROCEDURES

8.4.1 ADVERSE EVENT REPORTING

All AEs will be recorded on the appropriate CRF and will include information about the start and stop dates, severity and relatedness. There should be an attempt to report a "diagnosis" rather than the individual signs, symptoms and abnormal laboratory values associated with the diagnosis. However, a diagnosis should be reported only if, in the Investigator's judgment, it is relatively certain (i.e., definite or possible). Otherwise individual signs, symptoms and abnormal laboratory values should be reported as distinct adverse events.

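### Section 7.3.2 implies that short-lived tenderness, edema and induration need no AE entry, while 8.3 and 8.4.1 require one, so the treatment-related AE count depends on the section a site follows

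*Combined protocol and SAP*

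**What the plan says.** Section 7.3.2, under Post Treatment, describes the reaction that sites should see: "The normal response to this treatment is transient tenderness, edema and/or induration in the treated area which should resolve within one to two weeks". The recording instruction follows at once: "If any other side effects occur or persist for longer than expected, they must be recorded in the adverse event (AE) section". Erythema is not on this list.

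Section 2.3.1 describes the same reactions differently: "Expected adverse events of the laser treatment procedure include transient tenderness, erythema, edema, and/or induration in the treated area lasting from one to three weeks". Section 8.2.3 repeats this almost word for word: "Expected adverse events of the treatment include transient tenderness, erythema, edema, and/or induration in the treated area lasting from one to three weeks". Both add erythema, both call the reactions adverse events, and both give a longer duration. Neither contains a recording rule.

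The recording rules are in 8.3 and 8.4.1. In 8.3, all AEs, "including local and systemic reactions not meeting the criteria for SAEs will be captured on the appropriate CRF", and "All AEs occurring while on study must be documented appropriately regardless of relationship". In 8.4.1: "All AEs will be recorded on the appropriate CRF and will include information about the start and stop dates, severity and relatedness". These two sections give no duration for local reactions and no exemption for expected ones.

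Subjects with a treatment-related AE are one of the two safety endpoints (4.2.2). Section 10.4.5 also reports the number and percentage of subjects with any AE.

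**The concern.** The same reaction falls under two recording rules. A coordinator working from the treatment-visit procedure in 7.3.2 would reasonably leave a few days of edema off the AE page, because the protocol has just called it normal and limited the mandatory entry to other or prolonged effects. A coordinator working from Section 8 would enter it.

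The choice reaches a declared endpoint. Under 8.2.2 an AE known to occur with the study treatment counts as related, so each entered reaction adds to the treatment-related AE count unless that subject already has another related AE. The study has a single arm, so the absolute percentage is the safety result and no control group shares the same under-recording. With up to five sites, the pooled percentage could be a mixture of two rules.

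**Working it through.** The plan states no AE rate, so there is no figure to reproduce. The check sets the rules side by side and then sizes the difference under a stated assumption.

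**Step 1: the possible rules.** The text allows three.
- Rule A: 8.3 and 8.4.1, with 8.2.3 making these reactions AEs. Every occurrence is entered.
- Rule B: 7.3.2 with its own window. Listed reactions are entered only if they last beyond two weeks.
- Rule C: 7.3.2, with the expected duration taken from 2.3.1 and 8.2.3. Listed reactions are entered only if they last beyond three weeks.

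**Step 2: apply them.**

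| Reaction in the treated area | Rule A | Rule B | Rule C |
|---|---|---|---|
| Tenderness, edema or induration ending within two weeks | entry | not required | not required |
| The same, ending in the third week | entry | entry | not required |
| The same, lasting beyond three weeks | entry | entry | entry |
| Erythema (not on the 7.3.2 list, so an other effect) | entry | entry | entry |

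The first row is the firm conflict. The second is a conflict only under Rule C. The last two give the same count under every rule.

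**Step 3: size.** Inputs: N = 50 subjects and 5 sites, the maxima in 5.3. Let p be the share of subjects whose only treatment-related AE is tenderness, edema or induration resolving within two weeks. The documents give no value for p, so a range is shown.

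Difference in the count, Rule A minus Rule B = N × p. Difference in the percentage = 100 × p points.

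- p = 0.10: 50 × 0.10 = 5 subjects, 10 points
- p = 0.50: 50 × 0.50 = 25 subjects, 50 points
- p = 0.90: 50 × 0.90 = 45 subjects, 90 points

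Under Rule C, p also takes in subjects whose only such reaction ended in the third week, so the difference is at least as large.

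**Step 4: one site.** With five equal sites of 10, a site that switches from Rule A to Rule B changes the pooled count by 10p, or 10p / 50 = 0.20p of the total. At p = 0.50 that is 5 subjects, or 10 percentage points, from one site.

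**Step 5: can the missing entries be recovered later?** The next scheduled visit is Week 6 ± 3 days, so day 42 − 3 = 39 at the earliest. That is 39 − 14 = 25 days after the two-week window closes and 39 − 21 = 18 days after the three-week window. Section 5.3 promises regular contact for retention but specifies no assessment of reactions. The length of a reaction would rest largely on recall.

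**The case against.** The strongest defence is that 7.3.2 never forbids an entry. It says what must be recorded, and the exclusion of normal reactions is an inference. Section 8.2.2 adds that doubtful observations should be reported, and 8.3 and 8.4.1 cover all AEs, so the document read as a whole favours recording. It stands that the exclusion is only implied. The doubt provision does not settle the matter, because 7.3.2 removes the doubt by calling the reaction normal.

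A second defence is that local reactions are captured elsewhere. Edema and erythema are graded on the immediate-response form, discomfort is scored on the pain scale, and 14.1 mentions data on expected adverse reactions. But the form and the scale are Day 0 assessments, the form has no item for induration or later tenderness, and 10.4.5 summarises both apart from AEs. The category in 14.1 is neither defined nor given an analysis.

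Third, the safety endpoint is descriptive with no hypothesis (10.2), and 8.5 sets no numeric threshold on this rate. That is correct: no test or stopping boundary is affected. The reported percentage still is.

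Four stronger readings are tempting and are not supported:
- A reader might infer that severe reactions would vanish from the safety record. Section 7.3.2 covers a normal, transient response, and treating incapacitating tenderness as normal is strained. Edema and pain are graded on Day 0, and 7.8 separately escalates burns and pain beyond narcotics.
- A reader might count short-lived erythema as a conflict. It is absent from the 7.3.2 list and so recordable there, and an expected adverse event is still an AE under 8.3. The lists differ, but the count does not.
- A reader might say that any reaction ending in the third week is counted differently. Under the two-week window of 7.3.2 it is recordable, as it is under 8.3. Being expected under 8.2.3 does not exempt it. Only Rule C makes it matter.
- A reader might predict that the 7.3.2 count would fall to a handful of subjects. The documents give no rate, and erythema and the cooling effects in 8.2.3 (tingling, itching, numbness) would still be recordable as other effects.

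**Conclusion.** The point holds in limited form. Sections 7.3.2 and 8.3/8.4.1 give different AE counts for tenderness, edema or induration that resolves within two weeks. If the expected duration in 7.3.2 is borrowed from 2.3.1 and 8.2.3, they also differ for reactions ending in the third week. Following 7.3.2 lowers the treatment-related AE count and the any-AE summary; the direction does not depend on any assumption. The size does: it is 50p subjects for 50 treated, and p is not in the documents. It also assumes that affected subjects have no other recordable related AE, since one such event would count them under either rule. Separately, the three descriptions of expected local reactions disagree on duration and on erythema and must be reconciled. The documents do not show which duration is right, and this review takes no position on that.

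**What to change.** Two changes to the protocol text.

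1. Reconcile 2.3.1, 7.3.2 and 8.2.3 so that they give one list of expected local reactions and one duration.
2. Replace the recording sentence in 7.3.2 with the rule already in 8.3 and 8.4.1. For example: record every local reaction in the treated area after treatment, expected or not, in the AE section of the CRF, with start date, stop date, severity and relatedness.

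Optionally, 10.4.5 could report expected local reactions on a separate line from other related AEs, so that common mild reactions do not hide the rest. This is a presentation choice and is not needed to remove the conflict.

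The cost is a wording change, site training, more AE entries and a less favourable overall AE percentage. No visit is added, so stop dates would still rest partly on recall at Week 6, and the study report should say so.

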4.2.2 SECONDARY ENDPOINTS

- To determine the change in thickness of the adipose layer as measured by ultrasound at twelve weeks post-treatment as compared to baseline
- To determine the change in abdominal circumference at twelve weeks post-treatment as compared to baseline
- To assess subject satisfaction with treatment at twelve weeks using the 5-Point Likert Subject Satisfaction Scale

Safety Endpoints:

- Report subject's assessment of discomfort and pain as measured by the Wong-Baker Faces Pain rating scale.
- Report subjects experiencing a treatment-related adverse event (AE).

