8.2.2 RELATIONSHIP TO STUDY AGENT

The clinician's assessment of an AE's relationship to the study agent is part of the documentation process, but it is not a factor in determining what is or is not reported in the study. If there is any doubt as to whether a clinical observation is an AE, the event should be reported. All AEs must have their relationship to study agent assessed. In a clinical trial, the study product must always be suspect. To help assess, the following guidelines are used.

- **Related** – The AE is known to occur with the study agent, there is a reasonable possibility that the study agent caused the AE, or there is a temporal relationship between the study agent and event. Reasonable possibility means that there is evidence to suggest a causal relationship between the study agent and the AE.
- **Not Related** – There is not a reasonable possibility that the administration of the study agent caused the event, there is no temporal relationship between the study agent and event onset, or an alternate etiology has been established.

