10.4.5 SAFETY ANALYSIS

The safety analysis will be done by analyzing spontaneous reports of adverse events (AE), subjects' completed 10 cm discomfort/pain visual pain scale and a response questionnaire as well as analysis of immediate response reports by the principal investigator from his/her observation/examination of the treated area. Appropriate Medical Dictionary for Regulatory Activities (MedDRA) code will be used to describe all spontaneously reported or other study related adverse events.

Summaries of spontaneously reported or other study related adverse events will be presented as:

- Number (%) of subjects with any AE,
- Number (%) of subjects with any serious adverse events (SAE),
- Number (%) of subjects permanently withdrawn from treatment due to AE

Summaries of analysis of immediate response reports by the principal investigator examination will be displayed on a bar or pie chart as;

- the overall frequency of subjects with each event (pain during treatment, hemorrhage, burn, erythema, edema, purpura)
- Frequency of subjects with specific severity/intensity for each event using a 5 points scale: 1=none; 2=trace; 3=moderate; 4=marked; 5=severe
- The overall percentage or proportion of subject observed with marked or severe intensity of any event will be calculated and compared to those with none, trace or moderate severity/intensity with the aid of a bar or pie chart.

The following will be considered for the analysis of 10 cm discomfort/pain visual pain scale scores safety data:

A summary table of the 10 cm discomfort/pain visual pain scale scores post treatment will be displayed as mean difference, standard deviation and standard error. The 10 cm discomfort/pain visual pain scale is a 11-level (0 to 10) ordinal scale tool for assessing pain.

The overall percentage or proportion of subject that recorded marked or severe post treatment discomfort/pain visual pain scale scores may be calculated and compared to those with none, trace, low or moderate discomfort/pain using a bar or pie chart.

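### Section 7.3.2 and sections 8.2.3 to 8.4.1 give different rules for recording brief tenderness, edema and induration, so the treatment-related AE count depends on which rule a site follows

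*Combined protocol and SAP*

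**What the plan says.** Section 4.2.2 lists two safety endpoints: pain, and subjects with a treatment-related AE. Two parts of the protocol decide who enters the second count.

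The visit instructions in section 7.3.2 (Post Treatment) state: "The normal response to this treatment is transient tenderness, edema and/or induration in the treated area which should resolve within one to two weeks". The next sentence sets the recording rule: "If any other side effects occur or persist for longer than expected, they must be recorded in the adverse event (AE) section" of the CRF.

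The safety section reads differently. Section 8.2.3 states: "Expected adverse reactions are AEs that are common and known to occur for the study agent being studied". It then names the reactions: "Expected adverse events of the treatment include transient tenderness, erythema, edema, and/or induration in the treated area lasting from one to three weeks". Section 8.3 requires that all AEs, "including local and systemic reactions not meeting the criteria for SAEs will be captured on the appropriate CRF", and it makes no exception for expected ones. Section 8.4.1 repeats that every AE is recorded, with dates, severity and relatedness. In section 8.2.2 the first ground for classing an AE as Related is "The AE is known to occur with the study agent". The same section says that an observation should be reported when it is doubtful whether it is an AE.

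Section 10.4.5 plans three AE rows: "Number (%) of subjects with any AE", the same for SAEs, and withdrawals due to an AE. None is split by relationship to treatment.

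**The concern.** A coordinator working from the visit instructions would reasonably leave on-time tenderness, edema and induration out of the AE section. One working from section 8 would enter each of them, and each would be Related by definition. The same subject could then count toward the safety endpoint at one site and not at another. If all sites followed 7.3.2, the total would fall short of what section 8 defines.

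No hypothesis test is at stake, because section 10.2 sets none for safety. What is at stake is the meaning of a declared safety endpoint in a pre-market study whose objective covers safety as well as efficacy. A reader of the final report could not tell which rule produced the number.

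**Working it through.** The plan states no figure to reproduce here. The check sets the two rules side by side and then identifies which subjects change status.

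**Step 1: the rules by reaction.** Inputs are sections 2.3.1, 7.3.2, 8.2.3, 8.3 and 8.4.1. Two weeks is Day 14 and three weeks is Day 21.

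| Reaction | 7.3.2 as written | 8.2.3, 8.3 and 8.4.1 |
|---|---|---|
| Tenderness, edema or induration, gone by Day 14 | No AE entry (implied) | AE, expected |
| Same three, gone on Days 15 to 21 | AE entry (past two weeks) | AE, expected |
| Same three, beyond Day 21 | AE entry | AE, longer than expected |
| Erythema, even if brief | AE entry (not in the 7.3.2 list) | AE, expected |
| Tingling, itching, decreased sensation, numbness (cooling) | AE entry | AE, expected |
| Burn, blister, pigment change, nodules | AE entry | AE |

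Only the first row changes whether an event is recorded. The second row changes only whether it is called expected. The two windows differ by 21 − 14 = 7 days. A site that took its meaning of longer than expected from 8.2.3 while applying the 7.3.2 rule would also leave out the second row.

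**Step 2: the effect on the endpoint.** Let N be the number treated (up to 50, sections 5.3 and 10.5). Let r be the number of subjects with at least one related AE that 7.3.2 would have recorded. Let s be the number whose only related reactions are tenderness, edema or induration that cleared on time.

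- Count under 7.3.2: r
- Count under 8.2.3, 8.3 and 8.4.1: r + s
- Difference: (r + s) − r = s
- Limit: 0 ≤ s ≤ N − r

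**Step 3: can s be given a value?** No. The documents report no rate for any of these reactions. The limit does not help without r. With N = 50, an assumed r of 5 would allow s up to 50 − 5 = 45, and an assumed r of 40 would allow at most 50 − 40 = 10. These values only show that the limit depends on a number the documents do not give. There is a reason to expect r not to be very small. Section 8.2.3 lists erythema as expected from both the laser and the cooling, along with tingling, itching, decreased sensation and numbness. Any subject with one of these already counts under 7.3.2, so is in r and not in s.

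**Step 4: the planned table.** Relatedness is collected for every AE (sections 8.2.2 and 8.4.1). The endpoint in 4.2.2 can therefore be derived from recorded data although 10.4.5 prints no row for it. The row inherits whichever recording rule was used.

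**The case against.** The strongest reply is that the documents, read together, favour recording. Section 7.3.2 says what must be entered and does not forbid entering the rest, and section 8.2.2 resolves doubt in favour of reporting. This softens the conflict without removing it. Section 7.3.2 is a specific instruction for the visit, and a site following it has no doubt to resolve. Its condition also has little purpose unless on-time reactions are exempt.

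A second reply is that the information may be held elsewhere. Section 8.3 speaks of the appropriate CRF, section 14.1 mentions expected adverse reaction data alongside AEs, and section 10.4.5 refers to a response questionnaire. The Day 0 immediate-response scale covers edema and erythema, but it omits tenderness and induration and is not scheduled again. No form described in the protocol captures brief tenderness or induration. However, the CRFs are not in the documents, so a reader who infers that the data would be lost for good goes further than the text allows.

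Three other stronger readings are tempting and not supported:

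- *That the related-AE rate would be understated by a large amount.* Both r and s are unknown, and s may be small.
- *That an extra contact before Week 6 is needed.* The first scheduled AE evaluation after Day 0 is at Week 6 ± 3 days (Day 39 to 45). Section 8.3 has the investigator ask at each visit about events since the last one and record onset and resolution, so the interval is covered, by recall. A call at about three weeks is a preference.
- *That important harms could go unrecorded.* Burns, blisters, pigment change, nodules, prolonged reactions and SAEs are recordable under either rule.

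**Conclusion.** The point holds as a conflict between two stated recording rules. A site that follows 7.3.2 as written would undercount the endpoint in 4.2.2 relative to the definitions in section 8. The undercount is exactly s subjects, a number the documents do not give and which may be small. The conclusion rests on reading the 7.3.2 sentence as an implied exemption for on-time reactions, and on no undescribed form feeding those reactions into the AE count. The differing windows (one to two weeks against one to three) and the absence of erythema from 7.3.2 are plain inconsistencies that leave no single cut-off for what is longer than expected. The missing row in 10.4.5 is minor, since it can be derived from collected relatedness. The change should be made, but no efficacy conclusion or hypothesis test depends on it.

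**What to change.** 1. In section 7.3.2, replace the recording sentence with a rule such as: *All local reactions after treatment, of any duration, are recorded as AEs with onset and resolution dates and flagged as expected or unexpected according to section 8.2.3.*
2. In section 7.3.2, use one to three weeks and add erythema to the list, to match sections 2.3.1 and 8.2.3.
3. In section 10.4.5, add the number (%) of subjects with at least one Related AE, split into (a) expected and resolved within three weeks and (b) unexpected or longer lasting.

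The cost is more AE entries. For the three reactions at issue this is at most 3 × 50 = 150, assuming one entry per reaction per subject. The total related-AE rate will look higher, which is why the split in item 3 is needed. The change to 7.3.2 is a protocol amendment that needs IRB approval under section 13.2, and the new recording rule helps only subjects treated after it takes effect. No new visit is required.
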